The incidence of prematurity is a health care crisis with significant economic and emotional costs in the United States (US) and worldwide. One of every 9-10 babies in the US²⁹, and an estimated 15 million babies worldwide^{29;30} are born preterm each year. Complications from preterm births are the leading cause of neonatal mortality and an important contributor to child and adult morbidities. In the US, the yearly estimated costs associated with preterm births are \$26.2 billion³¹⁻³³. All preterm infants have altered lung development with a high incidence of wheezy respiratory illnesses, hospitalizations, and asthma compared to full term infants³⁴. In preterm infants <37 weeks with and without BPD in the first year of life, the incidence of cough was reported to

be 79%, wheezing 44%, and respiratory re-hospitalizations $25\%^{35}$. A recent study in 537 infants born at < 28 wks gestation reported that 65% had post discharge respiratory disease and 71% had frequent wheeze or cough for \geq 6 months in the first year of life³⁶. *If eCPAP is demonstrated to stimulate lung growth and improve lung function, it could improve the respiratory health of up to 500,000 preterm infants yearly in the US and millions of preterm infants worldwide.*

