Values are Mean ± SD; eCPAP= extended CPAP; CGA= corrected gestational age; RND= randomization; Avg=Average; *p<0.05 for the difference in the change in FRC between the CPAP and no CPAP infants by multiple linear regression with repeated measures and time treatment interaction adjusting for gender, twins, and weight at randomization.

Extended CPAP may constrain developmental therapies⁷⁷ and may affect intermittent hypoxic episodes which are common in preterm infants, underestimated by clinically used pulse oximeter settings, but have been associated with long-term neurodevelopmental problems⁷⁸⁻⁸⁰. The pilot eCPAP study had limited funding for the collection of detailed clinical respiratory and neurodevelopmental outcomes after discharge from the NICU. These outcomes will be explored in greater detail in the proposed study to provide data for a planned multicenter trial. In the pilot eCPAP study, 89% of the infants had a respiratory questionnaire done at 12 months of age with wheeze or cough without cold as per parent report³⁵ occurring in 58% of the infants in the eCPAP arm versus 73% in the CPAP discontinuation. This will be further studied with monthly respiratory questionnaires in the proposed study. Available Bayley neurodevelopmental scores at 6 months CGA from 29 of the 44 infants in the pilot study demonstrated the infants in the eCPAP arm had an average cognitive percentile score of 61.5% versus 46.7% in the CPAP discontinuation arm.

b3d. Sedation with Chloral Hydrate

Sedation with chloral hydrate is the standard for infant PFTs after 44 weeks of CGA as per the American Thoracic Society^{81;82}. [name] has IRB approval for sedation for PFTs at Oregon Health & Science University (OHSU) for term/preterm infants (current eIRB #386). In our recent RCT (Drs. [name], [name] Co-Pls; [name]) "Vitamin C to Decrease the Effects of Smoking in Pregnancy on Infant Lung Function (VCSIP)^{83;84}, chloral hydrate sedation was done in 220 infants at 3 and 12 months of age for a total of about 440 total pulmonary function tests. There were no serious adverse events due to sedation.

3. Rationale for a Randomized Clinical Trial

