Cohort retention will be maximized with the application of novel and evidence based retention techniques⁸³ as used in our previous VCSIP study which had a cohort retention of 93% at attempted 3 month PFTs⁸⁴ and 94% of infants with completion of respiratory questionnaires through 12 months of age as per protocol ⁸⁴. Techniques include regular multimodal contact such as phone calls and text messages, social media private messaging, and pre-arranged check-ins at mother or child's appointments. In instances where contact is difficult, alternative retention strategies are: searching databases for updated contact information; calling at different times of the day and on weekends; and contacting close friends and/or relatives who were listed by the participant as back-up contacts, or the participant's work if permission was obtained during consent.

h. Parent Questionnaire and Future Contact

At the completion of the study the parent will be asked to complete a series of questions adapted from the standardized Research Participant Perception Survey ⁹⁹ consisting of Likert scale items to assess their experience and satisfaction with the research study, team, and process.

We may contact subjects in the future if there are things we need to discuss or ask regarding this study or for future study opportunities, if they agreed on the consent form to this future contact. We will also review the subject's medical records in the future to look at breathing and behavior outcomes up to 24 months of age. We may also review and obtain other health information which may be important for the study. We may obtain this information so that we can be sure to have all of the important information we need for the study.

i. Adverse Event and Protocol Violation Reporting

Safety events requiring expedited reporting will be sent to the DSMB chair within 7 calendar days of learning of the event. The DSMB chair will respond to [name] (study PI) with recommendations within 14 calendar days.

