loss data from the pilot eCPAP study and from the VCSIP^{83,84} study. In the pilot eCPAP study 66% of parents whose infants met all inclusion and exclusion criteria consented to enrollment in the study. In this follow-up eCPAP study we are projecting that 50% of the parents whose infant meets all inclusion and exclusion criteria will consent due to the needed sedation at the 6 month PFT.

With regards to the exploratory clinical respiratory outcome, published data in 48 preterm infants with an average gestational age of 28 weeks who did not develop BPD (similar to the group we project to recruit) reported a 48% incidence of wheeze and a 79% incidence of wheeze and cough in the first year of life ³⁵. These researchers also documented a 21% incidence of wheeze in 195 term infants during the first year of life. In our initial vitamin C study⁴⁶ using the same questionnaire we will use in this proposed eCPAP study, 76 term infants born to non-smokers had a 27% incidence of wheeze in the first year of life. Based on these data, we project that 48% of the infants who have CPAP discontinued by the CPAP stability criteria will have wheeze in the first year of life. With our projected sample size of 50 per group accounting for a 15% missing questionnaire rate, we will

Figure 12: Projected Study Recruitment and Follow-up

have 70% power to show a decrease in the incidence of wheeze from 48% to 21% and 90% power to show a decrease in wheeze and cough from 79% to 50%.

b. Statistical Analysis

To verify the comparability of the randomized groups, infants' baseline characteristics will be compared using analysis of T-test or non-parametric Wilcoxon test for continuous variables and chi-squared test for categorical variables. We will examine the distributions of continuous variable and use alternative approaches such as transformation or nonparametric methods in cases of violation to the normal distribution assumption. We will examine the frequency distribution of all categorical variables and adopt exact inference procedures in cases of zero or small cell size. All analyses will be conducted using the SAS 9.4 (SAS Institute, Carey, NC).

b1. Specific Aim #1 (Primary Outcome)

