With regards to the exploratory clinical respiratory outcome, published data in 48 preterm infants with average GA of 28 weeks who did not develop BPD (similar to the group we project to recruit) reported a 48% incidence of wheeze in the first year of life 4 . These researchers also documented a 21% incidence of wheeze in 195 term infants. In our initial vitamin C study 5 using the same questionnaire we will use in this proposed eCPAP study, 76 term infants born to non-smokers had a 27% incidence of wheeze in the first year of life. Based on these data, we project that 48% of the infants who have CPAP discontinued by the CPAP stability criteria will have wheeze in the first year of life. With our projected sample size of 50 per group accounting for a 15% missing questionnaire rate, we will have 70% power to show a decrease in the incidence of wheeze from 48% to 21%, and 90% power to show a decrease in wheeze and cough from 79% to 50%.

Interim analysis and stopping rules. No interim analysis for efficacy is planned. There will be no prespecified stopping rules, but the DSMB will review SAEs as they occur. Although this is a fragile population, based on our pilot eCPAP study, the fact that infants will be convalescing by the time they are enrolled in the study, and our experience with sedation in the VCSIP, we do not anticipate a large number of SAEs but will be vigilantly monitoring. The DSMB chair may call a DSMB meeting to specifically review safety concerns.

References:

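### The 70% and 90% powers for the respiratory outcomes cannot both hold at one sample size, and the 79% *wheeze and cough* rate is undefined

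*SAP*

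**What the plan says.** The SAP bases both powers on one sample: "With our projected sample size of 50 per group accounting for a 15% missing questionnaire rate". On that basis it states "we will have 70% power to show a decrease in the incidence of wheeze from 48% to 21" per cent, and in the same sentence "90% power to show a decrease in wheeze and cough from 79% to 50" per cent. Protocol 7a makes the same two claims. Neither document gives a test, a significance level or a sidedness for them; alpha of 0.05 is stated only for alveolar volume.

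The base rates come from a published cohort of 48 preterm infants without BPD (protocol reference 35), which according to Protocol 7a "reported a 48% incidence of wheeze and a 79% incidence of wheeze and cough in the first year of life". The SAP repeats the 48% with its source but uses the 79% without one.

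The same reference appears in Protocol 2a for a wider group, preterm infants "with and without BPD in the first year of life, the incidence of cough was reported to" "be 79%, wheezing 44" per cent. The pilot result in Protocol 2, b3c, is for "wheeze or cough without cold as per parent report".

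SAP Specific Aim 3 and Protocol 7 b3 plan separate logistic regressions for wheeze and for *wheeze and cough*, adjusted for gestational age at delivery. The SAP appendix defines only the wheeze outcome.

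**The concern.** Two comparisons with the same number of infants, nearly the same absolute difference and nearly the same variance must have nearly the same power. A 20-point gap therefore suggests that the two figures came from different tests, sidedness or sample sizes, although the text presents them on one basis.

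The label is a separate problem. An infant with both wheeze and cough is an infant with wheeze, so the joint rate in a cohort cannot exceed its wheeze rate. Either 79% is something else (cough alone, or wheeze or cough) or the rate is wrong.

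Aim 3 is meant to supply pilot data for a later multi-center trial, whose planners may reuse these figures. If the tests are two-sided, the chance of missing the second effect is about 20% by pooled chi-square (16% to 27% across tests), not 10%. The second outcome also has a different event rate under each reading, so its result cannot be read clearly until it is defined.

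**Working it through.** **Inputs.** 50 per group and 15% missing (SAP): 50 × 0.85 = 42.5, so 42 to 43 evaluable per group. Rates 48% against 21% and 79% against 50% (SAP, Protocol 7a). Alpha 0.05 is an assumption for these outcomes, tried two-sided and one-sided.

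**Two-sided pooled chi-square.** With p̄ the mean of the two rates and d their difference,

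power = Φ{ [d√n − 1.96·√(2p̄(1−p̄))] / √(p1(1−p1) + p2(1−p2)) }, with √42.5 = 6.519.

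- Wheeze: d = 0.27, p̄ = 0.345. √(2 × 0.345 × 0.655) = 0.6723; √(0.2496 + 0.1659) = 0.6446. (1.760 − 1.318)/0.6446 = 0.687, so power is 75.4%.
- Second outcome: d = 0.29, p̄ = 0.645. √(2 × 0.645 × 0.355) = 0.6767; √(0.1659 + 0.25) = 0.6449. (1.891 − 1.326)/0.6449 = 0.875, so power is 80.9%.

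The variance terms are practically equal and the two normal deviates differ by 0.19. Powers of 70% and 90% correspond to deviates of 0.524 and 1.282, a difference of 0.76.

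**Other tests**, alpha 0.05, 42 to 43 per group, wheeze / second outcome:

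| Test | Two-sided | One-sided |
|---|---|---|
| Pooled chi-square | 74.9–75.9% / 80.4–81.4% | 84.1–84.9% / 88.3–88.9% |
| Unpooled z | 77.5–78.4% / 83.0–83.9% | 85.8–86.5% / 89.8–90.4% |
| Continuity-corrected | 66.7–67.9% / 73.2–74.4% | 77.6–78.7% / 82.9–83.8% |
| Fisher exact | 68.4–69.9% / 74.9–76.2% | 78.0–79.2% / 83.0–84.1% |
| Wald, log odds ratio | 72.1–73.1% / 77.4–78.3% | 81.6–82.4% / 85.7–86.4% |
| Wald, log relative risk | 68.2–69.2% / 75.0–76.0% | 78.5–79.3% / 83.9–84.6% |
| Arcsine | 75.6–76.5% / 80.9–81.8% | 84.3–85.0% / 88.3–89.0% |

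The likelihood ratio test, two-sided, gives 74.8–75.8% / 80.2–81.1%.

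**Reproducing the plan's figures.** The 70% is matched by two-sided Fisher at 43 per group (69.9%), where the second power is 76.2%. The 90% is matched by the one-sided unpooled test (89.8–90.4%), where the wheeze power is about 86%. No single test gives the pair.

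**Size of the gap.** Within any one test above it runs from 3.9 to 6.8 points. For the closed-form tests at alpha 0.05 it is at most 6.9 points for any n from 15 to 120 per group, and at most 8.7 points for alpha from 0.01 to 0.20. Changing the common sample size or alpha within these ranges does not produce 20.

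**Better retention.** Protocol 6g reports for the earlier trial "94% of infants with completion of respiratory questionnaires through 12 months of age as per protocol". At 50 × 0.94 = 47 per group, the two-sided pooled test gives 79.6% / 84.8%. With nothing missing (50 per group) the second outcome has 82% to 89% across the two-sided tests. Reaching 90% needs 52 (unpooled) to 64 (log relative risk) evaluable per group, and 56 by pooled chi-square.

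**The 79%.** Protocol 7a gives 48% wheeze and 79% *wheeze and cough* in the same 48 infants; taken literally, the second cannot exceed 48%. Protocol 2a attaches 79% to cough, with 44% wheezing, in a group that includes infants with BPD. The pilot used wheeze or cough. The documents do not settle which is meant.

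**Scoring.** The SAP appendix lists the answers that make an infant positive for wheeze and gives no rule for a second outcome. Its one cough item, question 10b (medicine for cough without a cold), feeds the wheeze outcome, and only when the medicine is a bronchodilator, steroid, leukotriene modifier or other listed wheeze medicine.

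**The case against.** The strongest reply is that the 70% may be right. The plan elsewhere assumes 10% loss in the NICU before the 15% loss, and questionnaires start after discharge: 50 × 0.90 × 0.85 = 38 per group. At 38 the two-sided pooled test gives 70.5% for wheeze. Twins point the same way: a design effect of 1.18 at 42 to 43 per group gives 67.5–68.6% and 73.4–74.5%. Replacing 70% by 75% could then overstate the wheeze power.

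This stands as a caution about which figure to change, but it does not rescue the pair. At 38 per group the second power is 76.3%, further from 90%. Taking 38 for wheeze and 50 for the second outcome gives 70.5% and 86.9%, close to both, but the text states one sample size with 15% missing.

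It is also fair that 75% and 80% belong to one choice of test, that nothing in the documents points to a one-sided test, and that *wheeze and cough* may be loose wording for a combined category. The Protocol 2a figures describe a different group, so they do not prove the 79% in 7a mislabelled. That leaves an ambiguity for the sponsor to settle from the source. Finally, the outcome is exploratory and these powers do not set the sample size.

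**Conclusion.** The concern holds. The stated powers differ by 20 points where one test at one sample size allows 4 to 7, so at least one is wrong. If the tests are two-sided at 0.05, the 90% is overstated: about 80–81% by pooled chi-square, 73–84% across tests, while wheeze is about 75–76% (67–78% across tests). If a one-sided unpooled 0.05 test was meant, the 90% roughly stands and the 70% should be about 86%. These figures assume alpha 0.05, 42 to 43 independent infants per group, and no gain from the gestational-age covariate, for which the documents give no figure. The 79% cannot be a joint rate beside 48% wheeze in the same infants, and the second Aim 3 outcome has no scoring rule. This is a text correction to an exploratory outcome; the sample size of 100 and the primary analysis are untouched. Because the analysing statistician is blinded, the issue is clarity rather than bias.

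**What to change.** In Protocol 7a and the SAP, restate both powers under one named test, alpha, sidedness and evaluable number per group:

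- On the stated 15% missing basis, a two-sided 0.05 chi-square gives about 75% (wheeze) and 80% (second outcome).
- If NICU loss or twin clustering was meant to count, say so. At 38 per group the same test gives 70.5% and 76.3%.
- If a one-sided 0.05 test was meant, declare it and give about 84–86% and 88–90%, depending on the variance used.

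Check in the cited publication what the 79% measures. Use one name for the outcome (both symptoms, either symptom, or cough alone) in Protocol 7a, Protocol 7 b3 and SAP Specific Aim 3, and recompute its power if the base rate changes. Add its scoring rule to the SAP appendix before unblinding.

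The cost is two or three sentences, one source check and one scoring rule, with no change to sample size, data collection or the primary analysis.

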Appendix: Clinical Respiratory Outcome

The wheeze outcome quantified between the infant's discharge from the Neonatal Intensive Care Unit through 12 months of age was obtained from the following specific questions contained on the standardized respiratory questionnaire^{1,2} which was administered monthly to the child's primary caretaker. A positive response to any of these questions on one or more respiratory questionnaire was recorded as a positive for the wheeze outcome. (The numbers below refer to the question number on the respiratory questionnaire and are organized by source: parental report; healthcare provider; medication use)

Field Label	Response Required/ Composite Notes (which to count)
PARENTAL REPORT	
Since [birth/the last time we talked] has your child had wheezing or whistling in his/her chest?	Any yes, ever. Include an overall count of individuals that answered yes as well as a second count of individuals that reported yes 2 or more times
14. Has child had any of the following illnesses?	14c. Bronchitis=1 (Yes)
	14d. Bronchiolitis=1 (Yes)
HEALTHCARE PROVIDER	
2. Since [birth/the last time we talked] has a health care provider said that your child has wheezy or asthmatic bronchitis?	Response = 1 (Yes)
3. Since [birth/the last time we talked] has a health care provider said that your child has asthma?	Response = 1 (Yes)
18. Reason for hospitalization code	Response = 3 (Bronchitis) or 4 (Bronchiolitis) or 5 (Wheezing) or 8 (Asthma/asthma exacerbation)
19. Not counting hospitalizations, has [CHILD] been seen by a doctor or health care provider because of problems with wheezing, asthma, or wheezy or asthmatic bronchitis, since [birth/the last time we talked]? Include visits to an emergency room, a doctor's office, urgent care, or clinic.	Response = 1 (Yes)
MEDICATION USE	
4a. Since the last time we talked, OR in the last 12 months, which of the following types of medication has child been given?	4a1. Bronchodilator inhalers/nebulizers, pills, or syrups= 1 (Yes)
	4a2. Steroid inhalers/nebulizers= 1 (Yes)
	4a3. Leukotriene modifiers=1 (Yes)
	4a4. Steroid pills or liquids= 1 (Yes)
	4a6a. If other, specify medication types. Refer to wheeze_med1=1 (Checked)
10b. Has child been given any medicine for a cough when he/she did not have a cold?	10b1a. Bronchodilator inhalers/nebulizers, pills, or syrups= 1 (Yes)
	10b1b. Steroid inhalers/nebulizers= 1 (Yes)

Field Label	Response Required/ Composite Notes (which to count)
	10b1c. Leukotriene modifiers=1 (Yes)
	10b1d. Steroid pills or liquids= 1 (Yes)
	10b1f . If other, specify medication types. Refer to wheeze_med1=1 (Checked)
17. Specify other medications [1]	refer to wheeze_med1= 1 (Checked)
18c. Nebulizer/Inhaler (breathing) Treatment in Hospital?	Response = 1 (Yes)
If Other medication was used, medication was	Response = 1 (Yes)

[1] Other medications: albuterol, albuterol nebulizer, pills, or syrups, steroid inhalers, nebulizers, leukotriene modifiers, steroid pills or liquids

References:

253

254255

256

257

258

262

- 1.Ferris BG. Epidemiology Standardization Project (American Thoracic Society). *Am Rev Respir Dis* 1978;118:1-120.
